- Using our estimates of β_1 and its standard error, carry out a t-test for the hypothesis.
- Form a confidence interval for β_1 and show that the lower bound is above -3.0 seconds,
- Calculate the least squares mean (LSM) at the mean baseline TBUT for the contrast between treatment and control, and its associated confidence interval, and show that the lower bound is above -3.0 seconds.

We will use the third (LSM) method since it provides the most flexibility, also allowing exploratory analyses examining the effects of other covariates, contrasts between groups, etc.

As is standard practice in non-inferiority studies, all tests will be carried out at a one-sided $\alpha = 0.05$ (or equivalently, using two-sided 90% confidence intervals).

The MEIB endpoint will use the same model and the same testing methods. To demonstrate non-inferiority of the TearCare treatment to the LipiFlow control for MEIB we will test the null hypothesis that β_1 is less than the non-inferiority margin of 5 units:

$$H_0: \beta_1 \leq -5.0$$

$$H_A: \beta_1 > -5.0$$

The study will be a success if the non-inferiority null hypothesis is rejected for both TBUT and MEIB. No alpha adjustments for multiplicity are necessary.

If the two non-inferiority nulls are rejected then each will be re-tested for superiority (that is, against 0.0 instead of the non-inferiority margin). If the TearCare device is superior to the LipiFlow control for either endpoint (or both) it will be declared superior for that endpoint (or both).

The linear mixed effects models can be fit in SAS or R as follows:

In SAS:

```
Proc Mixed data=TearCare method=ml;
  class SUBJ TRT;
  model TBUT_DIFF = TRT TBUT_BL / solution;
  random intercept / subject=SUBJ;
```

In R:

```
library(lme4)
fit.tbut <- lmer(TBUT.DIFF ~ TRT + TBUT.BL + (1|SUBJ) ,
  REML=FALSE, data=TearCare)
```

Note that since we are interested in testing the fixed effects, ML (maximum likelihood) versus REML (residual maximum likelihood) estimates are being used.

If the estimated between-subject variance $\hat{\sigma}_a^2$ is close to 0 we will repeat the analysis without the random intercept term (that is, as a standard ANCOVA without a random patient effect).

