There are different options for calculating the standard errors/confidence intervals. Standard diagnostic tests and plots for outliers, normality of the errors, homogeneity of variances, and homogeneity of slopes will be provided. Based on prior data there is every reason to expect that the TBUT and MEIB errors will be approximately normally distributed. However, if residuals do not appear sufficiently normally distributed, we will calculate the confidence interval for β_1 using bootstrap methods.

If the ANCOVA model is unsatisfactory (e.g. linearity of change with respect to baseline is not supported, or the slopes are different) then we will test the primary hypotheses and compute the confidence interval for the difference in change from baseline between the two treatments based on a LME model without the baseline covariate (i.e. a t-test with adjustment for correlation).

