22.3.1 TEAR BREAKUP TIME

For the TBUT sample size calculation, we assume the same positive treatment effect for TearCare and for LipiFlow, reducing the TBUT time per eye by 3 seconds, with a standard deviation of 6.0 seconds. The standard deviation for the change from baseline to 1 month was (conservatively) estimated for TearCare from the pilot data, and for LipiFlow from published results⁵⁵.

The sample size is calculated under the following assumptions:

- a one-sided $\alpha = 0.05$ t-test for non-inferiority,
- with a NI margin of 3.0 seconds,
- to obtain 95% power.

The non-inferiority margin was based on published LipiFlow variability⁵⁵. Under these assumptions the required sample size is 176 eyes, 88 eyes per treatment group.

The design effect for a clustered sample when randomization is at the cluster level is calculated as $DEFF = 1 + \delta(m - 1)$ where δ is the intraclass correlation and m is the

⁵⁴ Campbell M, Walters, S. How to Design, Analyse and Report Cluster Randomised Trials in Medicine and Health Related Research. Wiley UK, 2014.

⁵⁵ Lane, S.S, H.B. DuBiner, R.J. Epstein, P.H. Earnest, J.V. Greiner, D.R. Hardten, E.J. Holland, M.A. Lemp, J.E. McDonald II, D.I. Silbert, C.A. Blackie, C.A. Stevens, and R. Bedi. A New System, the LipiFlow, for the Treatment of Meibomian Gland Dysfunction. Cornea 2012; 31(4): 396-404.

average size of the clusters in the sample⁵⁶. Here $m=2$ so $DEFF = 1 + \delta$. To estimate the intraclass correlation we fit a linear mixed effects model with a random intercept for subjects to obtain estimates of σ_a^2 and σ_e^2 . Using these we can estimate the intraclass correlation as $\delta = \sigma_a^2 / (\sigma_a^2 + \sigma_e^2)$. From the TearCare pilot data the estimates of the variance components for TBUT are $\hat{\sigma}_a^2 = 1.92$ and $\hat{\sigma}_e^2 = 3.39$, giving a DEFF of 1.36. We will assume that the intraclass correlation for LipiFlow is the same as TearCare. So the sample size calculated using the t-test formulas will be inflated by 1.4 to account for correlation between eyes. Thus the DEFF-adjusted sample size is 246 eyes.

Finally, we will assume that 10% of the enrolled subjects (eyes) will be lost to follow-up. The resulting sample size is 274 enrolled eyes, or 137 enrolled subjects (which we round up to 69 per group).

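### Fitting the primary models by ML makes the deciding 90% confidence intervals slightly too narrow: about 1% in the planned model, more only if centre is added with many centres

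*Combined protocol and SAP*

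**What the plan says.** SAP section 22.1.1 models change from baseline per eye with treatment, baseline and a random subject intercept. The sample SAS code opens with "Proc Mixed data=TearCare method=ml" and the R call ends with "REML=FALSE, data=TearCare". The reason given is an interest in testing the fixed effects, so that "ML (maximum likelihood) versus REML (residual maximum likelihood) estimates are being used".

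The decision itself is made with an interval. Of three equivalent routes, the section selects the least squares mean contrast and its confidence interval, and non-inferiority requires the lower bound to lie above -3.0 seconds (TBUT) or -5.0 units (MEIB). On the level, "all tests will be carried out at a one-sided $\alpha = 0.05$ (or equivalently, using two-sided 90% confidence intervals". If both tests succeed, the same models are tested again against 0 for superiority.

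Neither code block names a degrees-of-freedom method. The section adds only that "There are different options for calculating the standard errors/confidence intervals", and it reserves the bootstrap for residuals that look non-normal.

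Section 22.1.2 tests treatment-by-centre with a likelihood ratio test on the same type of model. If it is significant at 0.15, a centre effect goes into the final model. Centres with fewer than 5 subjects are merged. Protocol section 7.2 allows up to 15 centres and at most 28 Cohort 2 subjects per centre.

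**The concern.** Comparing models with different fixed effects by likelihood ratio requires ML. A confidence interval for one contrast does not: it needs a good standard error. ML variance estimates make no allowance for the fixed effects that were fitted, so the standard error comes out too small. The lower bound is then too high, which makes non-inferiority, and after it superiority, easier to declare than the stated level allows. The error does not cancel across endpoints, since both have the same favourable direction, and it grows with the number of between-subject terms. Centre terms are where it could become noticeable.

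**Working it through.** **Inputs.** From SAP sections 22.3.1, 22.3.2 and 22.3.4: one-sided alpha 0.05; 95% power per endpoint; true difference 0; margins 3.0 s and 5.0 units; SDs 6.0 and 9.0; 138 subjects, 69 per arm; 10% loss. Evaluable subjects: 138 x 0.9 = 124. Between-eye correlation: TBUT 1.92/(1.92 + 3.39) = 0.36; MEIB 15.93/(15.93 + 20.11) = 0.44. Centres: 15 at most; 138/28 = 4.9, so at least 5 before any merging.

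**The plan's own figures.** For TBUT the plan sizes for a margin ("with a NI margin of 3.0 seconds") under a zero difference ("we assume the same positive treatment effect for TearCare and for LipiFlow"), "to obtain 95% power". The normal formula gives 2 x (6/3)^2 x (1.645 + 1.645)^2 = 86.6, so 87 eyes per group. The exact t calculation gives 88, as stated. MEIB: 2 x (9/5)^2 x 10.82 = 70.1, so 71, as stated. Both are reproduced.

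**Approximation.** With n subjects and p between-subject fixed parameters, the ML standard error is about sqrt((n - p)/n) of the unbiased one. The one-sided error rate is then P(t on n - p df > critical value x ratio). Two critical values were used: t on n - 1 df, roughly what the SAS code would use by default, and z = 1.645.

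- Base model, p = 2: sqrt(122/124) = 0.992. Then 1.657 x 0.992 = 1.644, giving 5.1% (5.3% with z).
- 15 centres, p = 2 + 14 = 16: sqrt(108/124) = 0.933. Then 1.657 x 0.933 = 1.547, giving 6.2% (6.4% with z).

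**Simulation.** 20,000 trials per setting, two eyes per subject, correlation 0.36, 124 subjects, the SAP model fitted by ML and by REML. The Monte Carlo standard error is about 0.15 percentage points.

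| Model | p | Ratio, formula | Ratio, simulated | Error rate, formula | Error rate, simulated |
|---|---|---|---|---|---|
| Base | 2 | 0.992 | 0.990 | 5.1-5.3% | 5.0-5.3% |
| + 5 centres | 6 | 0.976 | 0.973 | 5.4-5.6% | 5.2-5.3% |
| + 10 centres | 11 | 0.955 | 0.952 | 5.8-6.0% | 5.8-5.9% |
| + 15 centres | 16 | 0.933 | 0.931 | 6.2-6.4% | 6.5-6.6% |

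A separate simulation gave the same ratios and error rates of 5.1-5.3%, 5.1-5.2%, 5.9-6.0% and 6.4-6.5%. The 5-centre draw in the table ran slightly low by chance (its REML reference was 4.7-4.8%), so the formula is the better guide in that row.

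**The rule as written.** Adding the centre main effect only when the interaction test is significant gives an overall rate of 5.0%, 5.3% and 5.7% for 5, 10 and 15 centres. With no true interaction, the ML likelihood ratio test at nominal 15% fires in 18%, 25% and 34% of trials.

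**After the fix.** REML with a t reference on between-subject degrees of freedom gives 4.7-5.2% in every setting.

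**On the outcome scale.** With 62 subjects per arm, the TBUT standard error is sqrt(2 x 36 x 1.36/124) = 0.89 s and the 90% half-width is 1.657 x 0.89 = 1.47 s. A 1% error moves the bound by about 0.015 s against a margin of 3.0 s. For MEIB: sqrt(2 x 81 x 1.44/124) = 1.37, half-width 2.27, shift about 0.02 units against 5.0.

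**The case against.** The strongest reply is that the model actually pre-specified has only three fixed parameters, so the error is about 1% of a standard error and cannot plausibly change the conclusion. That stands.

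A reader might infer from the 15-centre row that the primary test runs well above 5%. The documents do not support this. Fifteen is a ceiling, small centres are merged, and centre enters only after a significant interaction test. The rate for the whole rule is the relevant figure.

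A reader might also infer that the interaction terms stay in the final model. With 15 centres that would give about 7.6-8.1%. Section 22.1.2 says that a centre effect is included and that results are reported by centre; it does not say that the overall contrast comes from a model with interaction terms.

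Nor is ML wrong throughout the plan: it is the proper method for the likelihood ratio test in section 22.1.2. The stated reason fits that test but not the interval.

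Finally, the code is offered as a way in which the models can be fitted, and the section leaves the interval method open. That means the degrees of freedom are unspecified, not wrong. It does not remove the ML bias, because the section's text also states that ML is being used.

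**Conclusion.** The point holds, at low severity. ML does not suit the interval that decides the trial, the bias favours the sponsor, and nothing else in sections 22.1.1 or 22.1.2 corrects it. The size is about 1% of the standard error and a one-sided rate of 5.1-5.3% in the base model. If centre is added, the rate is 5.1-5.6%, 5.8-6.0% or 6.2-6.6% with 5, 10 or 15 centres, and the whole rule stays at about 5.0-5.7%.

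These figures assume 124 evaluable subjects, the TBUT between-eye correlation, a between-eye correlation of 0.5 at baseline, equal-sized centres and treatment balanced within centre. The actual number and sizes of centres are not in the documents, which is why a range is given. The finding does not show that the non-inferiority test is unsound, nor that the trial is too small.

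**What to change.** In section 22.1.1, specify REML (SAS `method=reml`; R `REML=TRUE`) with Kenward-Roger or between-subject degrees of freedom for all least squares mean contrasts and 90% intervals, covering both non-inferiority and superiority. Replace the sentence that justifies ML. Keep ML only for the likelihood ratio test of treatment-by-centre in section 22.1.2, and state there which centre terms remain in the final model. The missing-data argument in section 22.1.3 is worded around full maximum likelihood; REML does not invalidate it, but the wording should be aligned.

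The cost is a few code options and sentences, and an interval about 1% wider in the base model. The planned sample size is unaffected, because it already comes from a two-sample t-test.

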At 1 month follow-up, TearCare subjects demonstrated an improvement from baseline in mean (\pm SD) TBUT of 11.7 ± 2.6 seconds compared with an average worsening of -0.3 ± 1.1 seconds for subjects in the warm compress group ($p<0.0001$). Significantly greater improvements in the change from baseline in meibomian gland scores, as well as corneal and conjunctival staining scores were observed in the TearCare group. Subjects in the TearCare group also showed significantly greater improvement in dry eye symptoms as measured by the three questionnaires.

No adverse events were reported in either group.

Table 2: TearCare System – Pilot Study Results (2017)

	TearCare (n=24 eyes, 12 subjects)			Warm Compress control (n=24 eyes, 12 subjects)		
	Baseline	4 weeks	6 months	Baseline	4 weeks	6 months
Tear Break-up Time (sec) – Mean (SD)	3.1 (0.8)	14.8 (2.6)	7.9 (1.5)	3.3 (1.0)	3.1 (0.8)	3.0 (1.0)
Dry Eye Symptom Questionnaires						
Total OSDI Score (0 to 100)	41.0 (18.4)	15.7 (12.2)	30.3 (15.1)	33.0 (19.9)	24.6 (15.2)	30.3 (15.1)
Total SPEED Score (0 to 28)	15.7 (5.2)	7.8 (3.5)	8.2 (6.0)	14.4 (3.8)	12.6 (3.3)	12.2 (4.0)
Total SANDE Score	64.9 (25.9)	40.2 (18.8)	45.9 (30.5)	55.9 (31.5)	57.5 (25.7)	62.1 (21.8)
Meibomian Gland Assessment						
Total Meibomian Gland Score (0 to 45)	6.3 (3.6)	41.0 (2.1)	31.5 (5.5)	9.0 (4.3)	8.2 (4.0)	9.4 (3.5)
# Glands Secreting Any Liquid (0 to 15)	0.8 (0.9)	14.6 (0.8)	11.5 (2.4)	1.3 (1.7)	1.3 (1.6)	1.7 (1.5)
# Glands Yield Clear Liquid (0 to 15)	0.0 (0.0)	11.4 (1.6)	5.4 (3.0)	0.3 (0.7)	0.0 (0.0)	0.1 (0.4)
Corneal Staining Score (0 to 15)	3.5 (1.8)	0.2 (0.4)	3.2 (2.6)	3.4 (2.9)	3.2 (2.6)	3.2 (2.8)
Conjunctival Staining Score (0 to 15)	3.7 (2.5)	0.1 (0.3)	0.3 (0.7)	3.0 (3.4)	4.1 (3.5)	3.2 (3.1)

Conclusions

The TearCare Group consistently showed a significant improvement between the baseline and 4 weeks follow-up for all outcome measures, whereas the Warm Compress group did not. For all outcome measures, the TearCare Group's mean change between baseline and 4 weeks follow-up was better than the Warm Compress group. These results were maintained out to 6 months.

This pilot study provided preliminary evidence of the safety and effectiveness of the TearCare device in relieving the signs and symptoms of dry eye.

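### The deciding test for both co-primary endpoints drops the baseline covariate on an undefined, data-driven trigger, although neither condition named biases the adjusted difference

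*Combined protocol and SAP*

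**What the plan says.** Section 22.1.1 of the SAP (Appendix B) models each eye's change at 1 month on treatment, that eye's baseline value and a random subject intercept. It sets this out for TBUT and adds: "The MEIB endpoint will use the same model and the same testing methods". Of three equivalent test methods it chooses the last: "Calculate the least squares mean (LSM) at the mean baseline TBUT for the contrast between treatment and control". The level is 0.05 ("As is standard practice in non-inferiority studies, all tests will be carried out at a one-sided" α), the margins are −3.0 seconds and −5.0 units, and both endpoints must succeed.

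On diagnostics it says: "Standard diagnostic tests and plots for outliers, normality of the errors, homogeneity of variances, and homogeneity of slopes will be provided". The fallback follows: "If the ANCOVA model is unsatisfactory (e.g. linearity of change with respect to baseline is not supported, or the slopes are different", the primary hypotheses are to be tested "based on a LME model without the baseline covariate (i.e. a t-test with adjustment for correlation". The two conditions are only examples. No test, cut-off, decision-maker or time of decision is given. Section 22.1.2, by contrast, fixes α = 0.15 for its own change of model (treatment by centre).

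Section 22.1.1 counts baseline adjustment as a source of power. Section 22.3 says the sample size leaves it out.

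**The concern.** In a randomised comparison the baseline covariate is there for precision. With 1:1 allocation, the adjusted difference still estimates the mean difference between arms when the relation with baseline is curved or differs by arm. Neither finding is therefore a reason to remove the covariate. The fallback replaces a line that fits imperfectly with a flat one, which fits no better.

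The rule governs the confirmatory test, not a sensitivity analysis, and the superiority re-test inherits it. A slope-homogeneity check needs the arms separated. With no criterion stated, two analysts could properly reach different deciding models from the same data. At stake are some width in the MEIB interval and, more importantly, a single deciding result fixed in advance.

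**Working it through.** **Inputs.** From 22.3: one-sided α 0.05; 95% power per endpoint; true difference 0; 10% loss. MEIB has SD 9, margin 5 and design effect 1.5. TBUT has SD 6, margin 3 and design effect 1.4. Enrolment is 69 per arm, so about 62 complete (69 × 0.9 = 62.1). Pilot baseline SDs (5.2.2, Table 2, row "Total Meibomian Gland Score (0 to 45" and the TBUT row) are 3.6 and 4.3 for MEIB, and 0.8 and 1.0 for TBUT. *Assumed:* slope of change on baseline of −0.5 to −1, and pilot SDs that carry over.

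**1. The plan's own figures.** Eyes per group = 2(1.645 + 1.645)² × SD²/margin².
- MEIB: 21.64 × 81/25 = 70.1, so 71. Then 142 × 1.5 = 213; 213/0.9 = 237 eyes; 119 subjects.
- TBUT: 21.64 × 36/9 = 86.6, so 87, or 88 with the t distribution. Then 176 × 1.4 = 246; 274 eyes; 137 subjects.

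Both match section 22.3, and both are unadjusted calculations.

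**2. Power under the fallback.** SE = SD × √(design effect/62).
- MEIB: 9 × √(1.5/62) = 1.40; 5/1.40 − 1.645 = 1.93; power 97.3%.
- TBUT: 6 × √(1.4/62) = 0.90; 3/0.90 − 1.645 = 1.68; power 95.4%.
- Joint, if independent: 0.973 × 0.954 = 92.8%.

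The stated power above 90% survives.

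**3. Precision lost.** Widening = 1/√(1 − r²) − 1, with r = slope × baseline SD/SD of change.

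| Endpoint | Baseline SD | Slope | r² | Interval wider by |
|---|---|---|---|---|
| MEIB | 3.6 | −0.5 | 0.04 | 2% |
| MEIB | 3.6 | −1 | 0.16 | 9% |
| MEIB | 4.3 | −1 | 0.23 | 14% |
| TBUT | 0.8 | −1 | 0.018 | 0.9% |
| TBUT | 1.0 | −1 | 0.028 | 1.4% |

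For MEIB at slope −1, the 90% half-width is 1.645 × 1.40 = 2.30 units unadjusted. Adjusted, it is 2.30 × √0.84 = 2.11 (baseline SD 3.6) or 2.30 × √0.77 = 2.02 (baseline SD 4.3).

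**4. Unequal slopes and curvature.** With equal arms, ANCOVA removes (average slope)² × baseline variance, so the loss from dropping baseline follows the average slope, not the slope difference. Slopes 0 and −1 average −0.5, which gives r² = 0.25 × 12.96/81 = 0.04, or 2%. Slopes +1 and −1 average zero, so nothing is lost.

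**5. Type I error.** MEIB was simulated on subject means with 62 per arm, a true difference of −5 and 8,000 trials per row (Monte Carlo SE 0.0024). The SDs of 3.6 and 9 were each multiplied by √0.72 for the mean of two eyes, since (1 + 0.44)/2 = 0.72. The rule was taken as 5% tests of the interaction and of a quadratic term. SEs are averages of the model-based values.

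| Slopes, LipiFlow / TearCare | SE unadjusted | SE ANCOVA | Switch triggered | Error: ANCOVA always | Error: fixed 5% rule | Error: more favourable model |
|---|---|---|---|---|---|---|
| −1 / −1 | 1.37 | 1.26 | 10% | 0.055 | 0.055 | 0.071 |
| −0.5 / −1.5 | 1.37 | 1.26 | 68% | 0.050 | 0.048 | 0.065 |
| 0 / −1 | 1.37 | 1.35 | 62% | 0.049 | 0.049 | 0.058 |
| +1 / −1 | 1.37 | 1.37 | over 99% | 0.052 | 0.052 | 0.056 |
| −1 / −1, curved | 1.37 | 1.26 | 97% | 0.049 | 0.049 | 0.066 |

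ANCOVA with one linear slope holds its level in every row, including those where its form is wrong. A model with interaction and quadratic terms gave 0.069 in the +1/−1 row when its model-based SE was used.

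**The case against.** The strongest defence is that the fallback is a single model, named in advance, and valid under randomisation for the same mean difference. Dropping baseline usually widens the interval, which makes non-inferiority harder to claim. The sample size never relied on adjustment. The higher error rates require someone to pick the more favourable model, which the SAP does not plan. All of that stands. It limits the harm, but it supplies neither a criterion nor a reason to drop the covariate.

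A reader might infer several stronger points that the documents do not support:

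- *Precision is always lost where baseline matters most.* This fits curvature with a steep slope. When slopes differ, the loss can be near zero (step 4).
- *The loss is 25% or more.* With the SD implied by the SAP's MEIB variance components, √(15.93 + 20.11) = 6.0, r² is (3.6/6.0)² = 0.36 and the widening is 25%. But unadjusted power is then above 99.9%. Applying the pilot TearCare SDs (3.6 and 2.1) would make the SD of change 1.7 to 2.0 times larger without baseline, but that rests on one arm of 12 subjects.
- *The pilot ceiling shows that slopes will differ.* Section 22.3.2 plans a 9-unit change in both arms, and the documents give no LipiFlow slope. If TearCare repeated its pilot gain of 41.0 − 6.3 = 34.7 against 9, it would lead by about 26 units and the margin of 5 would not be in question.
- *The choice is made after unmasking.* The SAP does not say when or by whom it is made. The gap is that silence.

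**Conclusion.** The point holds as a free improvement to the rule that decides trial success. The switch is unnecessary, and it costs a modest amount of MEIB precision and almost none for TBUT. Its trigger is open enough that control of type I error at 0.05 is not assured by the text. It does not undermine the stated power or make the fallback estimate invalid.

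The sizes rest on assumed slopes and on pilot baseline SDs. Inclusion criterion 6 caps baseline MEIB at 12 per eye, so the trial SD may differ; an even spread over 0 to 12 would give 12/√12 = 3.5. They also assume 62 completers per arm with no further per-protocol exclusions, and the simulation uses subject means rather than the two-eye model. The argument from randomisation applies to the Cohort 2 per-protocol population only so far as exclusions leave the arms comparable, and that caveat affects the adjusted and unadjusted models alike.

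**What to change.** In section 22.1.1, delete the fallback as a deciding test. State that the mixed-model ANCOVA with linear baseline, with the least squares mean contrast taken at the mean baseline of the endpoint concerned, is the single primary model for TBUT and MEIB whatever the diagnostics show. Keep the diagnostics as reported output.

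List three sensitivity analyses that do not decide success: a treatment-by-baseline model, a non-linear baseline model and the unadjusted model. In the interaction model, centre baseline at the overall mean and use a standard error valid for the contrast at that mean. The model-based one treats the observed mean as fixed, and it was too small in step 5 when slopes differed strongly. Interaction or non-linear terms should not be made conditional replacements for the primary model, since that would recreate the same data-driven choice.

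The separate provisions on bootstrap intervals and on a near-zero subject variance are not touched by this change. The cost is SAP wording only, with no effect on sample size, data collection or participants.
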